## STUDY OBJECTIVE

The primary objectives of this clinical study include:

- Evaluate clinical efficacy and performance of M2A Magnum in Asian population in comparison to competitors' similar products.
- Investigate potential advantages of M2A Magnum compared to M2A Taper (28mm and 32mm) in terms of Range of Motion, Dislocation while maintaining the same function improvement and pain reduction.
- Investigate Metal-ion release and renal function in M2A Total Hip Arthroplasty.

#### **DEVICE DESCRIPTION**

## M2A Magnum

The M2a-Magnum™ Large Metal Articulation is an ultra-high performance metal-on-metal articulation offering superior joint mechanic restoration and full compatibility with Biomet's clinically proven hip stems. Unlike ceramic-on-ceramic or traditional metal-on-polyethylene bearings, the M2a-Magnum™ system offers the stability and ROM of a big ball (≥38mm) in acetabulums as small as 44mm.

- Allows for significant wear reduction compared with metal or ceramic-on polyethylene and the potential for higher stability and range of motion (ROM)
- Features PPS® Porous Plasma Spray surface coating and full hemisphere geometry with four sets of paired fins
- Six neck length offsets from -6 to +9mm
- Available in shell sizes from 44-66mm (2mm increments) and head sizes 38-60mm (2mm increments)

## M2A Taper (28mm or 32 mm)

The M2a-Taper Acetabular System consists of a titanium outer shell with cobalt chromium (Co-Cr-Mo) metallic liner, which articulates with a cobalt chromium (Co-Cr-Mo) modular femoral head. The system is all metal – there is no polyethylene in the design.

The outer surface of the acetabular shell is covered with a porous coating of Titanium (Ti-6Al-4V) per ASTM-F136 which ensures immediate component fixation and maximum bone-to-implant contact. The plasma sprayed surface consists of particles which are bonded together to form a random pattern of interconnecting pores. The Co-Cr-Mo liner fits into the Ti outer shell by means of a taper. The locking mechanism consists of a three-degree taper with a maximum engagement of 0.075 inches. The shell has inner diameters of either 28mm or 32mm. The 28mm inner diameter is available in shell sizes 48mm through 70mm. The 32mm is available in shell sizes 52mm through 70mm.

Bi-Metric XR and Taperloc can be used with M2A Taper and M2A Magnum in the study.

#### STUDY DESIGN

The study is designed as a prospective, controlled multi-center study..

## Hypotheses:

Study Hypotheses are established based on the primary objectives. Specifically:

Hypothesis 1 – M2A Magnum will achieve the range of survivorships of competitors' products at 2 year postop (based on the only available information on competitors' products).

Hypothesis 2 – M2A Magnum will have better Range of Motion compared to M2A Taper (28mm or 32mm) at 1 year postop

Hypothesis 3 – M2A Magnum will have lower dislocation rate than M2A Taper (28mm or 32mm) at 5 year postop

Accordingly the study will include 2 subgroup studies. The relationship between the 2 subgroups is illustrated in the following table and graph:

Subgroup	Objectives	Trial Group	Control Group	Design	Endpoint(s)
1	Evaluate long term performance and size fit of M2A Magnum in Asian population and in comparison with competitors' similar products.	M2A Magnum .	Published data on Competitors' similar product – ASR.	Single arm cohort with Objective Performance Criteria (published data)	Survivorship, HHS, UCLA, Patient Satisfaction, cup seating, neck angle at immediate postop (part of radiographic assessment).
2	Compare early ROM, Clinical Outcomes, Metal-ion release and dislocation between M2A Magnum and M2A Taper w/ conventional head sizes	M2A Magnum	M2A Taper	RCT	HHS, ROM, UCLA, Dislocation and Metal-ion release, renal function, MRI Assessment[, survivorship

The study will be conducted over a period of 12 to 15 years. Patients from subgroups 1 and 2 will be followed at immediate postop, 3 months, 6 months, 1 year, 2 years, 3 years, 4 years, 5 years, 7 years and 10 years.

## PATIENT SELECTION

All subjects, regardless of sex, race, or geographic location, must fit into the scope of the Inclusion / Exclusion criteria to be eligible for the study. If required per applicable regulations, all participants must sign an Informed Consent to be enrolled into the study.

## **Inclusion Criteria**

Patients suitable for primary Total Hip Replacement

Patients with degenerative joint disease (inflammatory or non-inflammatory) or any of the composite diagnoses of:

- a. Osteoarthritis
- b. Avascular necrosis
- c. Legg Perthes
- d. Rheumatoid Arthritis
- e. Diastrophic variant
- f. Fracture of the pelvis
- g. Fused hip
- h. Slipped capital epiphysis
- i. Subcapital fractures
- j. Traumatic arthritis

Patients aged over 20 years old.

Patients with limited co-morbidity - ASA I - III

Patients must be able to understand instructions and be willing to return for follow-up Patients willing to provide blood and urine samples for metal ion analysis at follow-up

## **Exclusion Criteria**

Pre-existing metal implants

Absolute contraindications include: infection, sepsis, and osteomyelitis. Relative contraindications include:

1) uncooperative patient or patient with neurologic disorders who are incapable of following directions,

2) osteoporosis,

3) metabolic disorders which may impair bone formation,

4) osteomalacia,

5) distant foci of infections which may spread to the implant site,

6) rapid joint destruction, marked bone loss or bone resorption

apparent on roentgenogram, and

7) vascular insufficiency, muscular atrophy, or neuromuscular disease.

8) pregnancy

#### **ENDPOINTS**

	SUBGROUP 1	SUBGROUP 2			
PRIMARY ENDPOINTS*	Survivorship at 2 year postop	Dislocation (5 year postop), Range of			
		Motion at 1 year postop.			
SECONDARY	At all follow-up visits:	At all follow-up visits:			
ENDPOINTS	Survivorship up to 10 year	Survivorship up to 10 year (for			
	Harris Hip Score	Magnum arm)			
	Radiographic Assessment	Harris Hip Score.			
	Patient Satisfaction – EQ5D	Radiographic Assessment			
	UCLA	Patient Satisfaction – EQ5D			
	Complications including revisions	UCLA			
		Complications including revisions			
		Metal Ion release			
		MRI assessment to all available			
		patients at 5 year follow-up.			
		ADDITIONAL IMAGE ASSESSMENT FOR			
		SYMPTOMATIC PATIENTS			

\*For sample size calculations.

## **PARTICIPANT POPULATION (SAMPLE SIZE)**

Participant population is determined based on primary/secondary endpoints of each subgroup following superiority or non-inferiority methodologies. Minimum sample sizes are determined in order to prove the hypotheses.

Primary Endpoint Accumulative Dislocation Rate at 5 year postoperative Superiority test – time to event

Null Hypothesis: $H_0$  $p_t = p_c$ Alternative Hypothesis: $H_a$  $p_t = p_c + d$ 

 $p_t$  = accumulative dislocation rate (1.8%)[2] in the trial group (Magnum) at 5 year postoperative.

 $p_c$  = accumulative dislocation rate (6.5%)[2] in the control group (M2A Taper) at 5 year postoperative.

α = 0.025 Significance Level (97.5% confidence)

β = 0.20 80% Power

 $Z_{1-a/2} = 2.24$  $Z_{1-\beta} = 0.84$ 

N = 150 per group.

Due to nature of this endpoint (occurrence of dislocation), it is not expected there will be significant lost to follow-up and patients usually come back to their operating surgeons for complications if any.

Primary Endpoint Range of Motion at 1 year postoperative Superiority test

Null Hypothesis:	H 0	$\mu_t = \mu_c$				
Alternative Hypothes	is: H a	$\mu_t = \mu_c + d$				
$\mu_t$ : mean of ROM in the trial group at 1 year postoperative.						
$\mu_c$ : mean of ROM in the control group at 1 year postoperative.						
α = 0.025	Significance	Level (97.5% confidence)				
β = 0.20	80% Power					
$Z_{1-a/2} = 2.24$ $Z_{1-\beta} = 0.84$						
d = 3.3 (degrees)	Clinically Rel	evant Difference in ROM based on literature.				
ξ = 7.1	Estimate sta This value is literature	ndard deviation of ROM at 1 year postoperative. based on results (preop and 1 year postop) from				

N = 95 (including 7.5% lost to follow-up) per group

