#### RANDOMIZATION

Patients will be randomized to receive M2A Magnum (trial group), or M2A Taper (control group). Patients have an equal opportunity of being assigned to the trial group or control group. Specifically:

In case of unilateral patients, the affected side of hip will be randomized to one of two groups. In case of bilateral patients, both sides of hip will be randomized to the same device (M2A Taper or M2A Magnum).

The randomization will occur via a random number generator (manual or computer). Block randomization will be used. Blocks of K patients will be created where K = 4. The possible sequences are AABB, BBAA, ABAB and BABA. Two sets of randomization blocks will be followed by unilateral and bilateral patients respectively. For unilateral patients, A or B represents the device assigned to affected side of the hip. For bilateral patients, A or B represents the device assigned to both affected sides of the hip.

The doctor or other health care professional does not choose the participants for each group. For Patients satisfying inclusion criteria, randomization will occur by retrieving the next randomly generated group assignment.

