## INSTITUTIONS

there will be 5 sites recruiting 150 Magnum cases and 150 M2A Taper cases.

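### The dislocation sample size of 150 per group gives about 42% power, not the stated 80%; the plan's own inputs need about 340 per group

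*Combined protocol and SAP*

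**What the plan says.** The Endpoints section makes 5-year dislocation a primary endpoint of Subgroup 2, the randomised comparison. Hypothesis 3 is that Magnum has the lower rate.

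The Participant Population (Sample Size) section plans a superiority, time-to-event test. Its inputs are "accumulative dislocation rate (1.8%)[2] in the trial group (Magnum) at 5 year postoperative" and "accumulative dislocation rate (6.5%)[2] in the control group (M2A Taper) at 5 year postoperative", alpha 0.025, 80% power, and normal quantiles of 2.24 and 0.84. The result is "N = 150 per group", with no allowance for dropout because little loss is expected for this endpoint. The section opens by saying that "Minimum sample sizes are determined in order to prove the hypotheses".

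For range of motion, with the same alpha, power and quantiles, it states "N = 95 (including 7.5% lost to follow-up) per group".

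The Institutions section adopts the dislocation figure as the recruitment target: "there will be 5 sites recruiting 150 Magnum cases and 150 M2A Taper cases".

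**The concern.** A difference of 4.7 percentage points between two low event rates, at a critical value of 2.24, would normally need several hundred patients per arm. With 150 per arm the plan expects only 150 × (0.018 + 0.065) = 12.45 dislocations in total, which is few for a test at this level with 80% power.

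Dislocation has the larger of the two printed sample sizes, and that size equals the enrolment target. If it is wrong, the whole randomised comparison is sized on it. A reader who trusts the 80% would take a non-significant result as evidence against a difference, when that result would be the more likely outcome even if the assumed effect were real.

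**Working it through.** **Inputs**, all from Participant Population (Sample Size): p_t = 0.018, p_c = 0.065, difference 0.047, mean rate 0.0415; two-sided alpha 0.025 (2.24 is the 1 − 0.025/2 quantile; 2.2414 unrounded); power 80% (0.84; 0.8416 unrounded). Allocation is 1:1 (Randomization). No loss to follow-up is assumed.

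**1. Check on the reading: range of motion.** With d = 3.3 and SD 7.1:
n = 2 × (2.24 + 0.84)² × 7.1² / 3.3² = 87.8, and 87.8 / 0.925 = 94.9. This matches the stated 95, so the quantiles are meant as printed.

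**2. Dislocation as two proportions.**
- Pooled: n = [2.2414 × √(2 × 0.0415 × 0.9585) + 0.8416 × √(0.018 × 0.982 + 0.065 × 0.935)]² / 0.047² = (0.6322 + 0.2357)² / 0.002209 = 341 per group (340 with the quantiles rounded as printed).
- Unpooled: n = (2.2414 + 0.8416)² × 0.07845 / 0.002209 = 338 per group.

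**3. Dislocation as time to event.** Under constant hazards, HR = ln(0.982) / ln(0.935) = 0.270.
- Schoenfeld: 4 × 9.505 / (ln 0.270)² = 22.2 events; 22.2 / 0.083 = 268 per group.
- Freedman: 9.505 × (1.270 / 0.730)² = 28.8 events; 28.8 / 0.083 = 347 per group.
- Simulated log-rank test (exponential times, censoring at 5 years): power 72.5% at 268 per group and 82% to 83% at 340. Schoenfeld is therefore optimistic at this hazard ratio and event count.

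**4. Power at 150 per group.**

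| Method | Power |
|---|---|
| Pooled two-proportion: Φ[(0.047 × √150 − 0.6322) / 0.2801] = Φ(−0.20) | 42% |
| Unpooled two-proportion | 43% |
| Freedman | 42% |
| Simulated log-rank | 41% to 42% |
| Fisher exact | 32% |
| Schoenfeld: Φ[√(12.45 / 4) × 1.308 − 2.2414] = Φ(0.07) | 53% |

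**5. Other readings of alpha, per group.**

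| Alpha | Pooled | Schoenfeld |
|---|---|---|
| Two-sided 0.05 (= one-sided 0.025) | 282 | 221 |
| One-sided 0.05 | 222 | 174 |

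Solving for the alpha at which 150 gives 80% power: pooled z = (0.5756 − 0.2357) / 0.2821 = 1.205, two-sided alpha 0.23; Schoenfeld z = 2.308 − 0.842 = 1.467, two-sided alpha 0.14. Neither is compatible with the printed 2.24.

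**6. What 150 per group can show.**
- The expected split is 2.7 against 9.75 events. The nearest whole numbers, 3 against 10, give z = (7/150) / √(2 × 0.0433 × 0.9567 / 150) = 1.98. The unrounded expectation gives 0.047 / 0.0230 = 2.04. Both fall short of 2.24.
- If the assumed rates are observed exactly, the 97.5% interval for the difference is 4.7 ± 2.2414 × 2.29 = −0.4 to 9.8 points. At 340 per group it is 4.7 ± 2.2414 × 1.52 = 1.3 to 8.1 points.
- Against 1.8%, 80% power at 150 needs a control rate of about 10.2% (8.4% by Schoenfeld).

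**The case against.** **The required number depends on the formula.** The plan labels the test time to event and names no formula. Schoenfeld is standard for a log-rank test; it needs 268 per group and gives 53% power at 150, so a range of about 270 to 350 is fairer than one figure. The range should indeed be shown. It does not rescue the plan: 53% is still far from 80%, and simulation puts the log-rank test at about 42%, in line with the two-proportion result.

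**The sponsor may hold an unprinted derivation.** This cannot be excluded. A figure near 150 appears at one-sided alpha 0.10 (148 by arcsine, 162 pooled). A one-sample test against a fixed 6.5% needs about 160 at two-sided 0.05, and about 200 at the printed critical value. The first contradicts the printed 2.24; the second contradicts the randomised two-arm design.

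**Reproducing range of motion clears only range of motion.** This is correct. Of the two calculations printed, one reproduces and one does not. Nothing follows for 2-year survivorship, for which the section prints no calculation.

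**Reporting mainly by confidence interval is a preference.** This also stands. The arithmetic requires only that N, power and assumptions agree.

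**Conclusion.** The error holds. At the plan's own inputs the dislocation comparison needs about 340 per group, and the stated 150 gives about 42% power against a claimed 80%. The most lenient formula gives 268 per group and 53%.

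The conclusion takes the 1.8% and 6.5% as printed; their source was not available to check. It also assumes no loss to follow-up. The plan gives no attrition figure for this endpoint. If, purely as an assumption, 7.5% to 20% were lost by 5 years under constant hazard, simulated log-rank power would be about 40% to 37%.

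This must be corrected, because the stated power is wrong for a primary endpoint whose N is the enrolment target. The estimate and its interval would still be informative at 150 per group.

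**What to change.** In Participant Population (Sample Size), replace the 80% power statement for dislocation with text such as:

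> With 150 per group, power is about 42% for 1.8% versus 6.5% at two-sided alpha 0.025, before any loss to follow-up; 80% power is reached only for about 1.8% versus 10.2%. The difference in 5-year cumulative dislocation will be reported with its 97.5% confidence interval, and a non-significant result will not be taken to show no difference.

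Qualify the section's opening claim about minimum sample sizes so that it no longer covers dislocation. This is a wording change and needs no extra patients; the cost is a less favourable stated power.

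To keep the 80% claim, the sponsor must do one of two things:
- raise N to about 340 per group here and in Institutions, which is about 190 more per group and 380 in total; or
- print the formula and assumptions that yield 150 and reconcile them with the printed critical value of 2.24.

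A separate clarification is worth making in the same edit: say whether 150 counts patients or hips. Institutions counts cases, while Randomization assigns both hips of a bilateral patient to one device. This does not explain the 150.

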## PARTICIPANT DATA MANAGEMENT

	PRE	OP	IMMEDIATE	3	6	1	2	3	4	5	7	10
	- O P	•	POST-OP	MO	MO	YR	YR	YR	YR	YR	YR	YR
Informed	x						X *					
Consent	~						~					
Demographic												
and Historical	Х											
Record												
Operative		v										
Record		^										
Metal ion												
concentrations	v			v	v	v	v	v	v	v	v	v
in blood and	^			^	^	^	^	^	^	^	^	^
urine												
Renal function												
(Creatinine	X			Х	X	Χ	Х	Χ	Χ	Х	Х	Χ
Clearance Test)												
Harris Hip Score	×			v	v	×	×			×		v
(Including ROM)	^			^	^	^	^			^		^
Postoperative				Y	Y	Y	Y			Y		Y
Thigh Pain				^	^	^	^			^		^
EQ5D	X			X	X	Χ	Χ	Χ	Χ	Χ	Χ	Χ
UCLA Activity	Y			Y	Y	Y	Y	Y	Y	Y	Y	Y
Score	^			^	^	^	^	^	^	^	^	^
Radiographic	x		x	x	x	x	x	x	x	x	x	x
Assessment	^		~	^	^	^	^	~	^	^	^	^
MRI										Y		
Assessment												
Additional	As needed											
Image	(for symptomatic patients only: having pain/discomfort on hip, higher ion											
Assessment	concentration than 7ppb or suspect of ARMD etc)											
(MRI / CT)	RI / CT)											
Complications &		Anytime										
Revisions												

The following table summarizes data collection required during the course of the study.

\* Informed consent will be obtained at the time of 2 year follow-up to continue to participation of the study.

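### The 80% power stated for 5-year dislocation makes no allowance for loss and is not delivered by 150 per group: the plan's own inputs give about 43% to 53% before any loss, and loss lowers this modestly

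*Combined protocol and SAP*

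**What the plan says.** The section PARTICIPANT POPULATION (SAMPLE SIZE) labels the dislocation endpoint "Superiority test – time to event". It takes "accumulative dislocation rate (1.8%)[2] in the trial group (Magnum) at 5 year postoperative" and "accumulative dislocation rate (6.5%)[2] in the control group (M2A Taper) at 5 year postoperative", with alpha 0.025 (z = 2.24), 80% power and 150 per group. No loss allowance is added, on the ground that "it is not expected there will be significant lost to follow-up and patients usually come back to their operating surgeons for complications if any".

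For range of motion at 1 year, in the same randomised comparison, the same section gives "N = 95 (including 7.5% lost to follow-up) per group".

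The footnote to the schedule in PARTICIPANT DATA MANAGEMENT reads "Informed consent will be obtained at the time of 2 year follow-up to continue to participation of the study". No refusal rate is given. INSTITUTIONS plans 150 Magnum and 150 M2A Taper cases, so nothing is held in reserve above the calculated number. No section says how patients lost before 5 years enter the dislocation analysis.

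**The concern.** A plan that expects some patients to be missing at 1 year should expect at least as many to be missing at 5 years, particularly when everyone is asked at 2 years whether they wish to continue. The reason given for expecting little loss is that patients usually return to their surgeon with complications. That bears on whether a dislocation comes to notice. It does not show that patients remain under observation for 5 years.

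At stake is the credibility of the 80% power for a primary endpoint. About 12 dislocations are expected across both arms, so small losses of information matter, and a non-significant result could be misread as evidence of no difference. With the handling of leavers unwritten, the 5-year rates could also be calculated in more than one way once the data are known.

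**Working it through.** **Inputs**, all from PARTICIPANT POPULATION (SAMPLE SIZE) unless noted:
- dislocation rates 1.8% and 6.5%, difference 0.047
- z = 2.24 and 0.84, so (2.24 + 0.84)² = 9.4864
- 150 per group
- range of motion: difference 3.3, SD 7.1, loss 7.5%
- re-consent at 2 years (PARTICIPANT DATA MANAGEMENT)

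Loss rates of 15% and 20% are assumptions, used to show a range.

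**1. Range of motion reproduces.** n = 2 × 9.4864 × 7.1² / 3.3² = 87.8, so 88 per group. 88 × 1.075 = 94.6, so 95, as stated. The 7.5% is a real allowance.

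**2. The 150 for dislocation does not reproduce.**
- Two proportions, unpooled: variance sum = 0.018 × 0.982 + 0.065 × 0.935 = 0.07845; n = 9.4864 × 0.07845 / 0.047² = 337 per group. The pooled form gives about 342, and 383 with continuity correction.
- Log-rank (Schoenfeld): hazard ratio = ln(0.982)/ln(0.935) = 0.270, log −1.308; events = 4 × 9.4864 / 1.308² = 22.2; per group 22.2/(0.018 + 0.065) = about 267, or 277 after rounding up to 23 events. Freedman's formula gives 29 events, about 349 per group.

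The requirement before loss is therefore roughly 270 to 380 per group.

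**3. Power at 150 per group, no loss.**
- Two proportions: 0.047/√(0.07845/150) = 2.055; 2.055 − 2.24 = −0.185; power 43% (42% in the pooled form).
- Log-rank: events = 150 × 0.083 = 12.45; (√12.45/2) × 1.308 = 2.308; 2.308 − 2.24 = 0.068; power 53%.

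**4. Effect of loss.** Suppose a fraction L leaves at 2 years and is censored, with dislocations even over 5 years (assumption). Leavers lose three fifths of their expected events, so events = 12.45 × (1 − 0.6L). The last two columns show the harsher case in which leavers contribute nothing, so n = 150 × (1 − L).

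| Loss | Events, censored at 2 years | Log-rank power, censored | Log-rank power, leavers dropped | Two-proportion power, leavers dropped |
|---|---|---|---|---|
| 0 | 12.45 | 53% | 53% | 43% |
| 7.5% | 11.89 | 51% | 49% | 40% |
| 15% | 11.33 | 48% | 46% | 37% |
| 20% | 10.96 | 47% | 43% | 34% |

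**5. Inflating 150 alone does not help.** 150/0.925 = 162.2, so 163 per group, still far below the number in step 2.

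**The case against.** The plan gives a reason for treating the two endpoints differently, and it has some force. Range of motion exists only if the patient attends; a dislocation can be reported between visits. The schedule records complications and revisions at any time. COMPLICATIONS (ADVERSE EVENTS) names operative-side dislocations and any event needing hospital or outpatient care, without restricting it to the study site. MONITORING PLAN has overdue follow-up chased. For patients still in the study, dislocations treated elsewhere are thus already reportable. The text also says no significant loss, not none, and the re-consent carries no refusal rate. All of this stands, and it is why the omission is unsupported rather than contradictory. It does not cover patients who decline at 2 years, for whom the plan describes no further collection.

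A reader might infer from the rationale that leavers are counted as free of dislocation, which would pull both rates towards zero. The documents do not say so. The time-to-event label points to censoring, and the rule is simply absent. A reader might also suspect bias that differs between arms; no section supports that.

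Finally, alpha 0.025 might be read as one-sided. The stated z of 2.24 is the two-sided value. Even one-sided, power at 150 with no loss is only about 53% (two proportions) or 64% (log-rank).

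**Conclusion.** The point holds as a wrong power figure resting on an unsupported assumption about loss. Under the plan's own rates and z, 150 per group delivers about 43% (two proportions) or 53% (log-rank), not 80%, before anyone leaves. Most of the shortfall arises because 150 does not follow from the stated inputs. Loss is the smaller part: with departure at 2 years and censoring, it costs about 2 percentage points of log-rank power at 7.5% and about 6 at 20%. The lower two-proportion figures of 40% to 34% apply only if leavers are dropped entirely.

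These results assume that the plan's two rates are correct, that dislocations fall evenly over 5 years, and that large-sample formulas are adequate with about 12 events. The last is rough, so the figures should be read as approximate. The conclusion that power is well below 80% does not depend on the choice among these methods.

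**What to change.** In PARTICIPANT POPULATION (SAMPLE SIZE), dislocation endpoint:

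1. Delete the statement that significant loss is not expected.
2. Replace the 80% with the power that 150 per group delivers under the plan's own rates and alpha, allowing for at least the plan's own 7.5% loss. Name the test used. On the figures above this is about 51% for a log-rank test with departure at 2 years and censoring, or about 40% for two proportions with leavers dropped. Do not merely inflate 150 and keep the 80%.
3. In the same edit, state that patients who are lost or who decline re-consent are censored at last contact and are not counted as dislocation-free at 5 years.

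The cost is a few sentences and a less favourable stated power. Enrolment, visits and case report forms are unchanged.

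### Primary ROM at 1 year: the plan names no model that uses pre-op ROM or the laterality stratum, and adjusting for both would tighten the estimate at the cost of wording only

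*Combined protocol and SAP*

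**What the plan says.** - **Hypotheses** states only the direction and the time: "M2A Magnum will have better Range of Motion compared to M2A Taper (28mm or 32mm) at 1 year postop". **Endpoints** lists ROM as a Subgroup 2 primary endpoint ("Motion at 1 year postop") without naming the motion or a test.
- **Participant Population (Sample Size)** gives a superiority test with equal means under the null. The Magnum mean is the "mean of ROM in the trial group at 1 year postoperative", and the control mean is defined in the same way. The inputs are alpha 0.025 with z = 2.24, 80% power, a difference of 3.3 degrees and an SD of 7.1. The result is "N = 95 (including 7.5% lost to follow-up) per group". The SD is labelled as that of 1-year ROM, but is said to be "based on results (preop and 1 year postop) from" the literature.
- **Participant Data Management** schedules the Harris Hip Score, which includes ROM, both pre-op and at 1 year.
- **Randomization** stratifies by laterality: "Two sets of randomization blocks will be followed by unilateral and bilateral patients respectively". In a bilateral patient "both sides of hip will be randomized to the same device".
- **Metal Ion Analysis** and **Renal Function Analysis** are each to be done separately by laterality. Nothing comparable is said for ROM.
- **Inclusion Criteria** admits fused hips and, as item "i. Subcapital fractures", a diagnosis for which a pre-op ROM may not be obtainable.

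The text available for review has no statistical analysis section, and no part of it names a t-test, ANCOVA, change score or covariate for ROM.

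**The concern.** A primary continuous endpoint has a scheduled baseline measurement and a known randomisation stratum, and neither is assigned to its analysis. Two things are at stake.

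1. **Precision.** If pre-op and 1-year ROM are correlated, adjusting for pre-op ROM narrows the interval for the treatment difference without adding a patient.
2. **An open choice.** Unadjusted, baseline-adjusted and change-score analyses would all fit the wording of Hypothesis 2 and can give different intervals. How to treat patients whose pre-op ROM cannot be measured is also open. Both decisions are better made before the data are seen.

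**Working it through.** **Inputs from the plan.** Difference d = 3.3, SD = 7.1, alpha = 0.025 two-sided (z = 2.24, or 2.2414 unrounded), power 80% (z = 0.84), 7.5% loss (all Participant Population); 150 recruited per arm (Institutions).

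**Assumed, because the plan does not give them.** The pre/post correlation r; the share of bilateral patients and their mean ROM difference from unilateral patients; the share with no usable pre-op ROM; and the same 7.5% loss applied to 150, although the plan states it only for N = 95.

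**Step 1: reproduce N.** n = 2 × (2.24 + 0.84)² × 7.1² / 3.3² = 87.8 per arm, and 87.8 / 0.925 = 94.95, so 95. This is the plain two-sample formula. A one-sided test at 0.025 would give 73, or 79 after loss, which does not match. The sizing contains no baseline or stratum term.

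**Step 2: unadjusted comparison at planned recruitment.** 150 × 0.925 = 138.75, taken as 139 evaluable per arm.
- Standard error = 7.1 × √(2/139) = 0.852.
- 97.5% half-width = 2.2414 × 0.852 = 1.91 degrees.
- Power for 3.3 degrees = Φ(3.3/0.852 − 2.2414) = Φ(1.63) = 94.9%.

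**Step 3: adjust for pre-op ROM.** Residual SD = 7.1 × √(1 − r²). The equivalent gain in patients is 1/(1 − r²).

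| r (assumed) | Half-width (degrees) | Power | Equivalent extra patients |
|---|---|---|---|
| 0 (unadjusted) | 1.91 | 94.9% | none |
| 0.1 | 1.90 | 95.1% | 1% |
| 0.3 | 1.82 | 96.6% | 10% |
| 0.6 | 1.53 | 99.5% | 56% |

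If 7.1 is really an SD of change (equal variances at the two times assumed), the absolute widths move but the relative narrowing is the same: 1.61 to 1.54 at r = 0.3, and 2.13 to 1.71 at r = 0.6.

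**Step 4: how far the open choice reaches.** With SD 7.1 at both times and r = 0.3, a change score has SD 7.1 × √(2 × 0.7) = 8.40. Its half-width is 2.26 degrees and its power 84.9%, against 1.91 and 94.9% unadjusted and 1.82 and 96.6% with ANCOVA.

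**Step 5: laterality alone.** Residual variance = 7.1² − p(1 − p)D², where p is the bilateral share and D the mean difference between strata. With p = 0.111 and D = 2 the half-width is 1.90; with p = 0.25 and D = 4 it is 1.85.

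**Step 6: unusable baselines.** Let 10% of patients have no usable pre-op ROM.
- Complete cases: n = 139 × 0.90 = 125.1 per arm. The half-width is 1.92 at r = 0.3, no better than unadjusted, and 1.61 at r = 0.6.
- All patients kept with a missing indicator: SD = 7.1 × √(0.10 + 0.90 × (1 − r²)). The half-width is 1.83 at r = 0.3 and 1.57 at r = 0.6.

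**The case against.** The strongest reply is that little is really open. The sample-size section already implies a reference analysis, a comparison of 1-year means, and a later switch away from it would be visible. That comparison is valid in a randomised trial and has ample power. At r = 0.1 the gain is negligible, and if adjustment costs 10% of patients it can leave the interval slightly wider than before (1.92 against 1.91 at r = 0.3). The laterality term is worth very little. It is also not established that the pre-op ROM item is the same motion, in the same degrees, as the endpoint behind the 3.3-degree difference.

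Most of this stands, and it limits the weight of the point. It does not remove it. A sizing formula is not a stated analysis, the loss of patients is avoidable by a rule set in advance, and the question of which motion is meant has to be settled for the endpoint itself in any case.

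A reader might infer four stronger things that the documents do not support:
- *That the plan rules out adjustment.* It is silent; the section concerned only sizes the trial.
- *That the ROM result would be biased, or that N = 95 is wrong.* The unadjusted test is valid, leaving out a balanced stratum is generally conservative, and N = 95 reproduces.
- *That ROM must be analysed separately by laterality because metal ions and renal function are.* Those statements concern those outcomes only.
- *That two hips of one patient will be counted as independent, inflating the type I error.* The plan randomises patients and nowhere says it will do this; it only omits to state the unit for ROM.

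**Conclusion.** The point holds as an improvement that costs almost nothing, not as an error. For primary ROM the plan specifies a comparison of 1-year means and gives no role to pre-op ROM or the randomisation stratum. What is lost is precision: nothing of note at r = 0.1, about 5% of interval width at r = 0.3 (1.82/1.91) and about 20% at r = 0.6 (1.53/1.91). Nearly all of it comes from pre-op ROM rather than from laterality. The choice between models is also left open. Power is not in question, at about 95% without adjustment. These sizes rest on assumed values of r, on the 7.5% loss carrying over to 150 per arm, and on pre-op ROM being recorded as the same measure as the endpoint.

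**What to change.** State in the plan, before outcome data are examined:

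1. The primary ROM analysis is an ANCOVA of 1-year ROM on treatment, pre-op ROM and the unilateral/bilateral stratum, tested at the planned two-sided 0.025.
2. Which motion, in which units, is the endpoint, and that the pre-op covariate is the same measure.
3. One value per randomised patient, for example the mean of both hips in bilateral patients.
4. Patients with missing or unmeasurable pre-op ROM are kept by simple imputation with a missing indicator. Define unmeasurable in advance and apply the definition without reference to treatment arm.

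The unadjusted comparison of 1-year means can be reported as a supporting analysis. The cost is analysis wording and one rule for unusable baselines. N = 95 for ROM does not change. No new data are needed, provided the scheduled pre-op Harris Hip Score assessment records the named motion in the same units; that should be checked against the case report form.
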